### Safety Assessment

Patients will not be allowed to participate or will be withdrawn if at any point in the trial they are found to be at high risk for suicide. Patients who provide an affirmative response (checks 1, 2 or 3) on Question 12 of QIDS will be referred and evaluated by a UH/Seidman Psychiatrist to assess whether high risk for suicide is present. Patients who are severely or moderately severely depressed by QIDS ( $\geq 16$ ) or PHQ-9 greater than 14 will be referred and evaluated by a UH/Seidman psychiatrist. They will not be discontinued from the trial, but may be offered additional therapy as part of standard of care, according to the judgement of the evaluating psychiatrist.

For a referral to a Psycho-Oncology Provider call [REDACTED] or email [REDACTED], [REDACTED]

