### **6.3 Duration of Follow-Up**

#### **End of Treatment Study Procedures**

An end of treatment visit will be conducted on Day 85 (Week 13). This will be a clinic visit and will include a physical exam, collection of pill diary and any unused pills, toxicity assessment, QIDS-SR, PHQ-9, Fact-Hep and FIBSER. The patient's disease and treatment status will also be assessed.

During Week 25 (12 weeks after the end of treatment), a phone visit will be conducted which will include a toxicity assessment, QIDS-SR, PHQ-9, Fact-Hep and FIBSER. Patients who screen above 11 on the QIDS-SR or above 9 on the PHQ-9 will be referred by the study team to a social worker, who will then conduct their own assessment and make appropriate referrals to psychiatry if necessary. Patients who give an affirmative reply to Question 12 on the QIDS-SR or 9 on the PHQ-9 indicating thoughts of suicide, will be referred to Seidman Psychiatry Service for evaluation (please see Section 7.0).

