**Table 7.1 Criteria for dosing delays and re-initiation of treatment due to study drug-related toxicity**

CTCAE Grade* Patient report or from any assessment scale	Dose Discontinuation Guidelines	
Hemorrhage (any site)	Grade 1: Mild symptoms; intervention not indicated Grade 2: Moderate symptoms; intervention indicated Grade 3: Transfusion indicated; invasive intervention indicated; hospitalization Grade 4: Life-threatening consequences; urgent intervention indicated	Grade 2 or greater: Discontinue drug, inform treating physician and PI immediately upon discovery.  (if this happens within first 4 weeks remove patient from study)
Suicidal ideation**	Grade 1: Increased thoughts of death but no wish to kill oneself Grade 2: Suicidal ideation with no specific plan or intent Grade 3: Specific plan to commit suicide without serious intent to die which may not require hospitalization Grade 4: Specific plan to commit suicide with serious intent to die which requires hospitalization	Grade 1-3: inform treating physician immediately upon discovery Grade 4: discontinue drug and remove from study.  See Table 7.2
Mania	Grade 1: Mild manic symptoms (e.g., elevated mood, rapid thoughts, rapid speech, decreased need for sleep) Grade 2: Moderate manic symptoms (e.g., relationship and work difficulties; poor hygiene)	Grade 3-4: discontinue drug and remove from study, notify treating physician and PI immediately.

	Grade 3: Severe manic symptoms (e.g., hypomania; major sexual or financial indiscretions); hospitalization not indicated; new onset  Grade 4: Life-threatening consequences, threats of harm to self or others; hospitalization indicated	
Hyponatremia	Grade 1: <LLN - 130.0 mmol/L  Grade 2: 125-129 mmol/L and asymptomatic  Grade 3: 125-129 mmol/L symptomatic; 120-124 mmol/L regardless of symptoms  Grade 4: <120 mmol/L; life-threatening consequences	Grade 4: discontinue drug and remove from study.
*CTCAE Version 5.0		
**Please see safety guidelines section below regarding patients exhibiting suicidal ideation		

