**Table 7.2 Suicidal Ideation Safety Guidelines**

Response to Question 12 on QIDS-SR*	Response to Question 9 on the PHQ-9	Action to be taken
0	0	No action
1	1	Immediately inform treating physician and PI*

2	2	Immediately inform social worker to perform assessment or send patient to ED (also inform treating physician and PI)*
3	3	Immediately inform social worker to perform assessment or send patient to ED (also inform treating physician and PI)*

\* If positive response discovered via phone assessment, clinical team must be informed within 4 hours. If a patient is at acute risk for self-harm, hospital/system suicide safety plan will be followed.

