## 8.2 Definitions

### 8.2.1 Adverse Event

An **adverse event** (AE) is any unfavorable or unintended event, physical or psychological, associated with a research study, which causes harm or injury to a research participant as a result of the participant's involvement in a research study. The event can include abnormal laboratory findings, symptoms, or disease associated with the research study. The event does not necessarily have to have a causal relationship with the research, any risk associated with the research, the research intervention, or the research assessments.

Adverse events may be the result of the interventions and interactions used in the research; the collection of identifiable private information in the research; an underlying disease, disorder, or condition of the subject; and/or other circumstances unrelated to the research or any underlying disease, disorder, or condition of the subject.

The measurement of side effects of escitalopram is not an endpoint of this study and escitalopram has been studied extensively in patients. This drug has also been studied as prophylactic antidepressant in the cancer populations. All patients enrolled to this study will be receiving chemotherapy at the time of treatment and will be under clinical care during this interval. Adverse events attributed to chemotherapy and/or underlying disease will not be recorded for this study.

Akathisia, or restlessness, is a serious but uncommon side effect, which patients will be alerted to report. Other common side effects typically go away on their own. Patients will be educated on possible symptoms, as is routinely done when patients are started on an anti-depressant off-of trial. They will contact the PI if the symptom becomes debilitating and referred to psychiatry for consideration of removal from the study.

Suicidal ideation will be queried every 2 weeks and prompt an immediate referral to psychiatry.

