#### **8.2.4 Adverse Events of Special Interest**

The following adverse events must be recorded, evaluated, and reported according to reporting policies of the IRB of record. Procedures related to these events will be followed as noted in Tables 7.1 and 7.2. Events are graded using CTCAE v5.0.

- Serious bleeding event (Grade 2 or greater). Will prompt discontinuation of escitalopram or placebo and removal from study.
- Mania. Symptoms consistent with mania will prompt referral to psychiatry.
- Suicidal ideation. Patients will be evaluated for suicidal ideation every 2 weeks using the QIDS and referred to psychiatry if present.

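### Section 7.0 requires psychiatric evaluation for any positive QIDS suicide-item answer, but the action tables in the same section list no such step

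*Combined protocol and SAP*

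**What the plan says.** Several places set a response to suicidal ideation.

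- **Section 7.0, Safety Assessment.** The trigger is an "affirmative response (checks 1, 2 or 3) on Question 12 of QIDS will be referred and evaluated by a UH/Seidman Psychiatrist". The stated purpose is to judge whether the patient is at high risk for suicide. The same paragraph bars or withdraws patients found to be at high risk, and Section 6.2 repeats the withdrawal.
- **Section 7.0, Table 7.2.** The table has one column for QIDS-SR Question 12, one for PHQ-9 Question 9 and one for the action. At answer 1: "Immediately inform treating physician and PI". At answers 2 and 3: "Immediately inform social worker to perform assessment or send patient to ED", with the physician and PI also told. A footnote allows four hours for informing the clinical team when the answer is found by phone, and invokes the hospital's suicide safety plan for acute risk.
- **Section 7.0, Table 7.1.** "Grade 1-3: inform treating physician immediately upon discovery". Grade 4 leads to discontinuation and removal. The cell also points to Table 7.2.
- **Section 8.2.1.** "Suicidal ideation will be queried every 2 weeks and prompt an immediate referral to psychiatry".
- **Section 8.2.4.** "Patients will be evaluated for suicidal ideation every 2 weeks using the QIDS and referred to psychiatry if present". The same section says that Tables 7.1 and 7.2 govern the procedures for these events.
- **Section 6.3, Week 25 paragraph.** Patients affirming QIDS-SR Question 12 or PHQ-9 Question 9 "will be referred to Seidman Psychiatry Service for evaluation", with a pointer to Section 7.0.
- **Section 1.2.** Patients with suicidal ideation go to a study psychiatrist.
- **Section 14.2, Treatment failures.** Suspected ideation is reviewed within four hours, citing Section 7.

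**The concern.** Table 7.2 is laid out as the working instruction: find the answer, read off the action. A coordinator who follows it exactly makes no psychiatric referral at any level. A coordinator who follows the paragraph just above it refers every patient answering 1, 2 or 3 on QIDS Question 12. Both are following the protocol.

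Patient safety is what is at stake. The psychiatric evaluation is the only procedure the documents give for deciding that a patient is at high risk for suicide, and that decision leads to withdrawal. If the evaluation is skipped because the table does not list it, the decision may not be made, or may depend on which part of the protocol a staff member uses.

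There is also a gap between instruments. The Safety Assessment paragraph's suicide-item trigger is QIDS Question 12 only, whereas Table 7.2 and Section 6.3 also use PHQ-9 Question 9.

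**Working it through.** The point depends on no power, alpha or sample-size figure, so the check is a comparison of the text.

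**Step 1: actions by answer, within Section 7.0.**

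| Answer | Safety Assessment paragraph (QIDS Q12) | Table 7.2 (QIDS Q12 and PHQ-9 Q9) |
|---|---|---|
| 0 | Referral not triggered | No action |
| 1 | Psychiatric referral and evaluation | Physician and PI notified |
| 2 | Psychiatric referral and evaluation | Social worker assessment or emergency department; physician and PI notified |
| 3 | Psychiatric referral and evaluation | As for 2 |

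The two agree at 0 and differ at each of the three positive levels.

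**Step 2: the other sections.** Sections 1.2, 6.3, 8.2.1 and 8.2.4 name psychiatry, as the paragraph does. Table 7.1 does not. For Grades 1-3 it names the treating physician alone, without the PI whom Table 7.2 adds. Table 7.1 works in CTCAE grades, and nothing maps a grade to an item answer.

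**Step 3: does any passage combine the two sets?** Section 8.2.4 comes closest, since it requires the referral and also invokes both tables. It does not say whether the referral is additional to the table's action, follows from it, or is summarised by it.

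**Step 4: answers that differ between the items.** Each item has four possible answers, giving 4 × 4 = 16 pairs. The rows of Table 7.2 show the 4 equal pairs, leaving 16 − 4 = 12 unlisted. Rows 2 and 3 carry the same action, so the pairs (2,3) and (3,2) are harmless. That leaves 12 − 2 = 10 pairs for which the table does not state how to act. Unequal answers are foreseeable: by the appendices, QIDS-SR covers the past seven days and PHQ-9 the past two weeks. An answer of 1 on QIDS Question 12 concerns life feeling empty or not worth living, while PHQ-9 Question 9 grades how often thoughts of death or self-harm occur.

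**Step 5: timing.** Table 7.2 and Section 14.2 both use four hours, but for different acts: informing the clinical team after a phone finding, and review by study staff. The two should be aligned in the same revision.

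**The case against.** The strongest reply is that the steps are compatible. The paragraph says who evaluates the patient and why; the table says who must be told at once. Nothing in Table 7.2 forbids referral, a patient can receive both, and Section 8.2.4 cites the referral and the tables together. On this view the table merely leaves out a step stated just above it.

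That reading is possible, and it rules out saying that the protocol anywhere tells staff not to refer. But no passage states it, and Section 6.3 weakens it. There, a raised total score goes to a social worker, who refers to psychiatry if needed, while a positive suicide item goes to the psychiatry service. These are separate routes, and Table 7.2 puts answers of 2 and 3 on the social-worker or emergency route. The footnote on acute risk is a real but partial safeguard: it does not say who evaluates the remaining positive answers.

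On differing answers, the two columns can be read as separate triggers. The higher row would then include the lower one's notifications, and the table would work. That is reasonable but also unstated.

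Two stronger readings are tempting and are not supported:

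- **A count of conflicts.** A reader might multiply the nine scheduled administrations (Days 1, 8, 22, 36, 50, 64, 78 and 85, and Week 25) by 55 patients and infer 9 × 55 = 495 occasions of conflict. That is a ceiling on screenings. The rules agree at answer 0, and the documents give no rate of positive answers.
- **Damage to the analysis.** A reader might infer bias through the treatment-failure label or missing data. In Section 14.2 that label leads to referrals and is not a term in the primary model. Sections 6.1, 6.2 and 7.0 largely keep discontinued or unblinded patients completing questionnaires; Section 7.0's first-four-weeks exception is a separate matter. No effect on the estimate is shown.

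**Conclusion.** The inconsistency is real and lies mainly inside Section 7.0. The Safety Assessment paragraph and four other sections require psychiatric referral for suicidal ideation; Table 7.2 lists none at any answer, and Table 7.1 lists none for Grades 1-3. The listed actions differ at three of the four answer levels. The paragraph's suicide-item trigger covers one instrument and the table covers two, without a stated rule for differing answers.

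The consequence is one of patient safety: staff acting from Table 7.2 alone could omit the evaluation that determines high suicide risk and hence withdrawal. This assumes only that the table may be used on its own, which its layout invites. How often this would happen cannot be estimated from the documents. No sample-size, power or alpha figure is affected. The change should be made, although the protocol is not without safeguards in the meantime.

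**What to change.** Reconcile Section 1.2, Section 6.3 (Week 25 paragraph), the Safety Assessment paragraph, Tables 7.1 and 7.2, Sections 8.2.1 and 8.2.4, and the treatment-failures text of Section 14.2 into one table. It should give:

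- the action for each answer on QIDS-SR Question 12 and on PHQ-9 Question 9;
- the action when the two answers differ;
- whether notification, social-worker or emergency assessment and psychiatric referral are cumulative or alternative, and in what order;
- how the CTCAE grades in Table 7.1 relate to the item answers;
- the time limit for each step.

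The other sections should then cite that table instead of restating the rule. Which action belongs in each cell is for the clinical investigators; this review proposes none. The cost is protocol wording and a notice to staff, with no new procedure required by the reconciliation itself.

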**Table 7.2 Suicidal Ideation Safety Guidelines**

Response to Question 12 on QIDS-SR*	Response to Question 9 on the PHQ-9	Action to be taken
0	0	No action
1	1	Immediately inform treating physician and PI*

2	2	Immediately inform social worker to perform assessment or send patient to ED (also inform treating physician and PI)*
3	3	Immediately inform social worker to perform assessment or send patient to ED (also inform treating physician and PI)*

\* If positive response discovered via phone assessment, clinical team must be informed within 4 hours. If a patient is at acute risk for self-harm, hospital/system suicide safety plan will be followed.

## 8.0 Adverse Events and Potential Risks

### 8.1 Escitalopram

Adverse side effects include:

Nausea (15%)  
 Ejaculatory disorder (9%)  
 Insomnia (9%)  
 Diarrhea (8%)  
 Dry mouth (6%)  
 Somnolence (6%)  
 Dizziness (5%)  
 Hyperhidrosis (5%)  
 Fatigue (5%)  
 Rhinitis (5%)  
 Influenza-like symptoms (5%)

Please refer to the escitalopram package insert for a comprehensive list of adverse events.

## 8.2 Definitions

### 8.2.1 Adverse Event

An **adverse event** (AE) is any unfavorable or unintended event, physical or psychological, associated with a research study, which causes harm or injury to a research participant as a result of the participant's involvement in a research study. The event can include abnormal laboratory findings, symptoms, or disease associated with the research study. The event does not necessarily have to have a causal relationship with the research, any risk associated with the research, the research intervention, or the research assessments.

Adverse events may be the result of the interventions and interactions used in the research; the collection of identifiable private information in the research; an underlying disease, disorder, or condition of the subject; and/or other circumstances unrelated to the research or any underlying disease, disorder, or condition of the subject.

The measurement of side effects of escitalopram is not an endpoint of this study and escitalopram has been studied extensively in patients. This drug has also been studied as prophylactic antidepressant in the cancer populations. All patients enrolled to this study will be receiving chemotherapy at the time of treatment and will be under clinical care during this interval. Adverse events attributed to chemotherapy and/or underlying disease will not be recorded for this study.

Akathisia, or restlessness, is a serious but uncommon side effect, which patients will be alerted to report. Other common side effects typically go away on their own. Patients will be educated on possible symptoms, as is routinely done when patients are started on an anti-depressant off-of trial. They will contact the PI if the symptom becomes debilitating and referred to psychiatry for consideration of removal from the study.

Suicidal ideation will be queried every 2 weeks and prompt an immediate referral to psychiatry.

### 8.2.2 Serious Adverse Events

A **serious adverse event** (SAE) is any adverse experience occurring at any dose that results in any of the following outcomes:

- Results in **death**.
- Is a **life-threatening** adverse experience. The term life-threatening in the definition of serious refers to an adverse event in which the subject was at risk of death at the time of the event. It does not refer to an adverse event which hypothetically might have caused death if it were more severe.
- Requires **inpatient hospitalization or prolongation of existing hospitalization**. Any adverse event leading to hospitalization or prolongation of hospitalization will be considered as Serious, UNLESS at least one of the following expectations is met:
  - The admission results in a hospital stay of less than 24 hours OR
  - The admission is pre-planned (e.g., elective or scheduled surgery arranged prior to the start of the study) OR
  - The admission is not associated with an adverse event (e.g., social hospitalization for purposes of respite care).

However it should be noted that invasive treatment during any hospitalization may fulfill the criteria of “medically important” and as such may be reportable as a serious adverse event dependent on clinical judgment. In addition where local regulatory authorities specifically require a more stringent definition, the local regulation takes precedent.

- Results in **persistent or significant disability/incapacity**. The definition of disability is a substantial disruption of a person’s ability to conduct normal life’s functions.
- Is a **congenital anomaly/birth defect**.
- Is an **important medical event**. Important medical events that may not result death, be life-threatening, or require hospitalization may be considered a serious adverse experience when, based upon appropriate medical judgment, they may jeopardize the subject and may require medical or surgical intervention to prevent one of the outcomes listed in this definition. Examples of such medical events include allergic

bronchospasm requiring intensive treatment in an emergency room or at home, blood disease or disorders, or convulsions that do not result in inpatient hospitalization, or the development of drug dependency or drug abuse. The development of a new cancer is always considered an important medical event.

### **8.2.3 Adverse Event Evaluation**

The investigator or designee is responsible for ensuring that all adverse events, (both serious and non-serious as defined in previous sections) observed by the study staff or reported by the subject that are determined to be related or possibly related to escitalopram/placebo which occur after the initiation of escitalopram/placebo are fully recorded in the subject's medical record and reported according to AE reporting policies of the IRB of record. Adverse events attributed to chemotherapy and/or underlying disease will not be recorded for this study. Source documentation must be available to support all adverse events.

The investigator or sub-investigator (treating physician if applicable) will provide the following for all adverse events (both serious and non-serious):

- Event term (as per CTCAE)
- Description of the event
- Date of onset and resolution
- **Expectedness of the toxicity**
- **Grade of toxicity**
- **Attribution of relatedness to the investigational agent- (this must be assigned by an investigator, sub-investigator, or treating physician)**
- Action taken as a result of the event, including but not limited to; no changes, dose interrupted, reduced, discontinued, etc. or action taken with regard to the event, i.e. no action, received conmed or other intervention, etc.
- Outcome of event

Descriptions and **grading scales** found in the NCI Common Terminology Criteria for Adverse Events (CTCAE) version **5.0** will be utilized for AE reporting.

**An expected adverse event** is an event previously known or anticipated to result from participation in the research study or any underlying disease, disorder, or condition of the subject. The event is usually listed in the Investigator Brochure, consent form or research protocol.

**An unexpected adverse event** is an adverse event not previously known or anticipated to result from the research study or any underlying disease, disorder, or condition of the subject.

**Attribution** is the relationship between an adverse event or serious adverse event and the study drug. Attribution will be assigned as follows:

- Definite – The AE is clearly related to the study drug.
- Probable – The AE is likely related to the study drug.
- Possible – The AE may be related to the study drug.

- Unlikely – The AE is doubtfully related to the study drug.
- Unrelated – The AE is clearly NOT related to the study drug.

Protocol must specify if attribution is required for individual components of the treatment regimen or the treatment regimen as a whole.

#### **8.2.4 Adverse Events of Special Interest**

The following adverse events must be recorded, evaluated, and reported according to reporting policies of the IRB of record. Procedures related to these events will be followed as noted in Tables 7.1 and 7.2. Events are graded using CTCAE v5.0.

- Serious bleeding event (Grade 2 or greater). Will prompt discontinuation of escitalopram or placebo and removal from study.
- Mania. Symptoms consistent with mania will prompt referral to psychiatry.
- Suicidal ideation. Patients will be evaluated for suicidal ideation every 2 weeks using the QIDS and referred to psychiatry if present.

